Integrated baroreflex assessment (LBNP) (Aim 1). After the modified Oxford protocol, we will assess integrated baroreflex function during incremental LBNP. Although low-level LBNP has been used to isolate cardiopulmonary baroreceptor input, arterial baroreceptors appear to be involved even at very low levels of LBNP (51, 96) so we use the term “integrated” to acknowledge the limitations of distinguishing cardiopulmonary versus arterial baroreceptor functions (23, 88, 103), and it is not the goal of these studies to distinguish the contributions of these respective baroreceptor inputs. **LBNP protocol:** During a 30-minute rest period after the SNP and PE infusions, microneurography electrode is removed, and subjects are instrumented in the left arm for the measurement of forearm blood flow (FBF, 87). We will measure baseline variables, tilt the subjects to 7° head down (HDT), return the subject to supine, then apply LBNP at -10, -20, -30 and -40 mm Hg (for 4 min each) in descending order. Heart rate, BP (beat-to-beat), PI and SkBF are measured continuously, and calf volume (circumference, to determine the extent of lower level volume shift and ensure relaxed muscles during LBNP). Blood sample is taken prior to and at the end of each stage of LBNP for the measurement of $S_{[ALD]}$, $S_{[ACE]}$, $S_{[ANG]}$, $P_{[Renin]}$, PRA, $P_{[ANG]}^{[1]}$, $P_{[NE]}$, $P_{[EP]}^{[1]}$. FBF is measured at 30-sec intervals, at rest and during the entire LBNP protocol. The total blood taken is 160 ml per visit. With FBF and BP data, we compute forearm vascular resistance (FVR) and conductance (FVC). If subjects experience presyncopal symptoms or if BP falls by 20% of baseline, we discontinue the study. If the test is stopped early we use the slopes generated from the completed levels of LBNP, but exclude data collected during symptoms or exaggerated BP falls. To determine peripheral vascular responses we analyze FVR and FVC as functions of LBNP. We will also determine changes in peripheral vascular responses by examining changes in HR as functions of SBP and LBNP (i.e. Δ HR/ Δ SBP or Δ LBNP). **LBNP** has been approved under HIC #0512000875.

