Statistical analyses: Univariate statistics [mean (SD)] will be generated on all study variables first, which will determine the normality or the heteroscedacity of the data. Data will be analyzed using SPSS 21 statistical software, that includes calculations to compensate for missing data, and Prism (GraphPad) curve fitting software where appropriate. **Data analysis.** The slopes of the linear regressions for PI-SBP (cardiovagal baroreflex gain), PI-LBNP (integrated baroreflex gain), resting MSNA, slopes for MSNA-DBP (sympathetic baroreflex gain during Oxford and Valsalva), will be compared between treatment conditions (GnRH antagonist vs. GnRH antagonist+T and between groups (Control vs AE-PCOS) using a 2-way repeated measures ANOVA with supplemental *post hoc* testing with Tukey's HSD test. **Sample size.** The desired statistical test is two-sided, and we assume an alpha level of =0.01 to account for multiple comparisons (37). In our laboratory, we observed effect sizes (SD) of PI-SBP intercept (with n=4) of 0.39 (0.16), our most stringent variable. A sample size of 15 women per group will allow us $\geq 80\%$ statistical power ($1-\beta > 0.9$) to test within group comparisons, and this same sample size will allow $[1-\beta]=0.80$ to distinguish any between-group differences from chance alone (29). Due to the technical challenges of performing microneurography on multiple occasions in obese women, we overestimate and account for a $\sim 20\%$ failure rate, so we will recruit 18 subjects per group. **R&R:** **1) GnRH antagonist suppression/hormone add-back** is the gold standard and most reliable method to control sex hormones in young women. **2) Microneurography** is the gold standard and most sensitive and reliable available measure for MSNA. **3) Lower body negative pressure** and the **Modified Oxford Technique** are the gold standards and most sensitive and reliable available measures of autonomic function in humans. We will report our methods and findings in detail and **full transparency** to permit others to reproduce and extend our findings. **Sex as a biological variable:** Only women are included in these studies because AE-PCOS is a female-specific disorder.

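### Under LBNP, a heart-rate index is labelled a peripheral vascular response, and one form of it divides by SBP change, which is itself an outcome (minor)

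*Combined protocol and SAP*

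**What the plan says.** The section on integrated baroreflex assessment (LBNP) for Aim 1 (Section V, Research Plan) steps chamber pressure through four levels: "then apply LBNP at -10, -20, -30 and -40 mm Hg (for 4 min each) in descending order". It gives two routes to peripheral vascular response.

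- The first is direct: "With FBF and BP data, we compute forearm vascular resistance (FVR) and conductance (FVC"), followed by "To determine peripheral vascular responses we analyze FVR and FVC as functions of LBNP".
- The second is added to it: "We will also determine changes in peripheral vascular responses by examining changes in HR as functions of SBP and LBNP". A parenthesis gives the form as ΔHR over the change in "SBP or Δ LBNP".

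The stopping rule is "If subjects experience presyncopal symptoms or if BP falls by 20% of baseline, we discontinue the study". After an early stop, slopes come from the completed levels, and data taken during symptoms or exaggerated pressure falls are left out.

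The statistical analysis text for Aim 1, repeated under Statistical Considerations, lists the outcomes for the repeated-measures ANOVA. It includes "PI-LBNP (integrated baroreflex gain") and the PI-SBP slope, the latter named as cardiovagal gain. It does not name ΔHR/ΔSBP.

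**The concern.** There are two separate problems.

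**Label.** An index whose numerator is heart rate describes the cardiac limb of the reflex. Reported as a peripheral vascular response, it would support a vascular conclusion that it cannot carry.

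**Denominator.** Under LBNP, SBP is not set by the experimenter. Its change depends on how well the woman defends her pressure, in part by vasoconstriction. Aim 1A hypothesises that androgen suppression alters α-adrenergic vasoconstriction, so the hypothesised effect can itself move the denominator. A group or treatment with a smaller SBP fall then shows a larger |ΔHR/ΔSBP| for the same heart-rate response, and a difference in pressure defence is read as a difference in reflex response.

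**Working it through.** **1. Consistency of the label (no assumptions).** The modified Oxford section and the Procedures text define the slope of PI on SBP as cardiovagal baroreflex sensitivity, and the analysis text uses the same name. HR is the reciprocal of PI. The same relation is thus cardiac in those places and vascular only in the LBNP sentence.

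**2. Stimulus or response.** In the modified Oxford test, drugs move BP about 15 mm Hg below and then about 15 mm Hg above baseline, so pressure is imposed. Under LBNP the imposed quantity is chamber pressure, fixed at 10 to 40 mm Hg below ambient, and ΔSBP is a result.

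**3. Arithmetic on the ratio.** The documents give no figure for ΔHR or ΔSBP under LBNP, so there is nothing of the plan's own to reproduce. All values below are assumptions. Take ΔHR = +12 bpm at -40 mm Hg in every woman:

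| ΔSBP (mm Hg) | ΔHR/ΔSBP | ΔHR/ΔLBNP |
|---|---|---|
| -3 | 12/(-3) = -4.0 | 12/(-40) = -0.30 |
| -6 | 12/(-6) = -2.0 | -0.30 |
| -12 | 12/(-12) = -1.0 | -0.30 |
| -24 | 12/(-24) = -0.5 | -0.30 |

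The SBP-based index spans a factor of 4.0/0.5 = 8 with no change in the heart-rate response.

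**4. False differences between groups.** Assumptions: ΔHR ~ N(12, SD 4) in both groups, ΔSBP normal and independent of ΔHR, and groups that differ only in mean ΔSBP. The evaluable n of 15 per group and the two-sided alpha of 0.01 come from the sample-size text. The test is a two-sample t-test, and the 20% stop is not applied as truncation.

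| Mean SBP fall, group 1 vs 2 (SD) | Rejects with single-point ΔHR/ΔSBP | Rejects with ΔHR/ΔLBNP |
|---|---|---|
| 6 vs 12 (2) | 79% | about 1% |
| 4 vs 8 (1.5) | 68% | about 1% |
| 12 vs 18 (3) | 48% | about 1% |
| 6 vs 12 (3) | 32% | about 1% |
| 4 vs 8 (3) | 3.2% | about 1% |
| 6 vs 12 (5) | 1.6% | about 1% |

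The nominal rate is 1%.

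**5. Slope instead of ratio.** If the index is each woman's regression slope of HR on SBP over the stages, with assumed stage noise of 3 mm Hg for SBP and 2 bpm for HR, false differences occur in about 1% to 6% of trials over the same scenarios. The slope is protected largely because noise in SBP pulls it towards zero. For an SBP fall of 2 its median is -0.47 against a true 12/(-2) = -6; for a fall of 20 it is -0.54 against 12/(-20) = -0.6. With less stage noise the slope would behave more like the ratio.

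**6. Stability of a raw ratio.** P(ΔSBP ≥ 0) = Φ(mean/SD).

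- Mean -2, SD 3: Φ(-0.67) = 25% wrong sign; 95% range of the ratio about -53 to +50.
- Mean -4, SD 3: Φ(-1.33) = 9%; range about -29 to +23.
- Mean -12, SD 3: Φ(-4), about 0; range about -2.3 to -0.3.

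Instability therefore needs SBP falls that are small relative to their SD.

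**The case against.** The strongest reply is that the index is supplementary and the remedy is mostly in the plan already. Forearm resistance and conductance against LBNP come first, PI-LBNP is the listed integrated gain, and ΔHR/ΔLBNP is offered in the same sentence. That stands, and it sets the severity. It does not remove the wrong label. Nor does it remove ΔHR/ΔSBP as a stated analysis, since the sentence does not say which denominator governs.

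Three stronger readings are tempting, and the documents do not support them.

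- **The denominator is near zero.** A reader might infer this from the stopping rule and the exclusion of large falls. A cap on large falls does not show that the remaining falls are small. With an assumed baseline SBP of 120, a 20% limit admits falls up to 0.20 × 120 = 24 mm Hg.
- **The planned ANOVA of this ratio is meaningless.** The ANOVA lists do not name the index. The wording about functions and slopes also allows a stage-wise slope, which does not produce exploding values.
- **The ratio has almost no power.** This holds only for part of the plausible range. With 30 per group, alpha 0.01 and HR rises of 10 vs 14 bpm (SD 4), power with the ratio is about 0.1% at mean ΔSBP -3 and 10% at -10 when the SD is 4. With SD 2 it is about 53% at -8 and 80% at -15. HR per mm Hg of LBNP gives about 88%.

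Instability and false differences also tend to occur in different conditions. With noisy falls near zero the t-test on the ratio rarely rejects. Frequent false differences need SBP falls that are clearly separated from zero.

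**Conclusion.** The concern holds as a minor one. The mislabelling and the use of a response as denominator follow from the protocol's own text. The consequence, a difference in ΔHR/ΔSBP with identical heart-rate responses, follows from the arithmetic. Its frequency is assumption-dependent: about 2% to 79% of trials for a single-point ratio and about 1% to 6% for a stage-wise slope, against about 1% for ΔHR/ΔLBNP. It rests on the assumed HR response, the assumed SBP falls and their SDs, the independence of the two, and the assumed stage noise. Instability and sign reversal of a raw ratio are conditional on small, variable SBP falls, which the documents neither show nor exclude. No listed ANOVA outcome, sample-size figure or primary sympathetic measure (MSNA) is affected.

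**What to change.** Revise the one sentence in the LBNP section:

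- drop ΔHR/ΔSBP as an index under LBNP;
- report HR or PI as each woman's regression slope on LBNP pressure, labelled integrated cardiac baroreflex response (PI-LBNP is already in the analysis list);
- take peripheral vascular response only from FVR and FVC against LBNP;
- report ΔSBP under LBNP separately, as an outcome in its own right.

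If the investigator prefers to keep ΔHR/ΔSBP, relabel it as cardiac, state whether it is a ratio or a slope, and prespecify how a small, zero or wrong-sign ΔSBP is handled.

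No new data, visits or procedures are needed. The cost is the loss of one supplementary index.

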PARTICIPANTS: For Aims 1, 1a, 2, 2a, two groups (n=36 each) of women will be recruited to complete this study: 1) IR, obese young women between the ages of 18 and 40 years (Controls); 2) IR, obese young women between the ages of 18 and 40 years with AE-PCOS. For Aim 3, two groups (n=16 each) of women will be recruited to complete this study: 1) IR, obese young women between the ages of 18 and 40 years (Controls); 2) IR, obese young women between the ages of 18 and 40 years with AE-PCOS. As women sign up for the study, they will complete medical histories, including the **Berlin questionnaire** (www.sleepmedicine.com) to screen for Obstructive Sleep Apnea (See Appendix 1). They will also fill out a hair growth chart. Subjects who smoke, have diabetes, sleep apnea or BP>140/90 will be excluded. Subjects will not be taking medications during the study, including any insulin sensitizing, CV medications, or hormonal contraception for at least four weeks prior to participating in these protocols. We do make exceptions for Tylenol in the event the subject has acute pain. All women (early proliferative phase in Controls) will undergo **3-hr oral glucose tolerance test (OGTT; 75 gram glucose load)** to determine IR (8). We define our subjects in both groups as having IR with AUC of glucose 140-200 mmol/L and AUC of insulin 40-90 μ U (57, 64). Sexually active participants will use barrier contraception for the duration of the study, and take pregnancy tests within 24 hours of participation. Subjects are excluded if they have lost > 5 kg of weight within the past 6 months or exercise more than three times/week. At their initial consent visit, after signing the consent form, subjects will be randomly assigned to take a GnRH antagonist with or without methyl testosterone (see “Study Design” below). They will be told immediately of the results of the randomization.

AE-PCOS subjects: Diagnosis of AE-PCOS will be based on modified NIH criteria requiring the presence of *both* **clinical hyperandrogenism** (hirsutism based on Ferriman Gallwey score of >8 and/or acne), and **biochemical hyperandrogenemia** (elevated serum total testosterone; ELISA,

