see Authentication). **Anovulation** (defined as a total of \leq 8 menses per year) and presence of **polycystic ovarian morphology** on transvaginal ultrasound as determined by a trained obstetrician/gynecologist ([name]), **obesity and IR** will be additional enrollment criteria for the AE-PCOS population. **Sex as a biological variable:** Only females will be used for these studies since AE-PCOS is a female-specific disorder.

Control subjects will be **obese, IR** women, with regular menses every 26-34 days. Subjects will be excluded if they have any symptoms of AE-PCOS subjects, including polycystic appearing ovaries (as determined by transvaginal ultrasound ([name])).

For Aim 1, 2 and 3: All subjects will be given urine collection containers to collect their overnight urine prior to visits 4,5 and 6.

For Aim 1, 2 and 3: All subjects will self administer Antagon injections for a total of 10 days. Subjects may be kept on Antagon for as long as 18 days if there is a challenge with experiment scheduling. Subjects will also ingest a testosterone pill for seven days. Subjects may also be kept on testosterone for up to 11 days with regard to scheduling issues.

For Aim 5: Subjects will participate in only one baseline study (Fig 7). We will recruit black and white women to participate in this study with AE-PCOS.

EXPERIMENTAL PROTOCOLS:

Aims 1 & 2. Study design (Fig 7) and Hormone administration (Fig 8): IR subjects with and without AE-PCOS will be randomly (MiniTab, © cleverbridge, Inc.) divided into two **Protocol** groups (4 groups total, n=18 each) to be tested 3 times each: **Protocol 1:** prior to GnRH antagonist (Day 1); GnRH antagonist (250 μ g/day in 0.5 ml normal saline, Days 3 and 10). **Protocol 2:** prior to GnRH antagonist (Day 1), GnRH antagonist alone (Day 3), GnRH antagonist + methyltestosterone (Day 10). In both Protocols, Day 1 in Controls occurs in the proliferative phase of the menstrual cycle (days 1-7, low hormone phase); GnRH suppression begins on days 26-28 of that cycle. Non-cycling women with AE-PCOS begin testing at their convenience.

*Women may take the Antagon pills for as long as 18 days. We allow this flexibility because of challenges with scheduling subjects. There is no increase in risk, and we do everything possible to avoid the rare instance where taking this drug needs to be extended. If the drug is extended, "day 10" procedures occur on the final day of "GnRH antagonist + methyltestosterone" administration.

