Characterization of the RAS during LBNP in humans (Aim 2). We will use the protocol described in **Fig 7** with the hormone intervention described in **Fig 8**. Before beginning the protocols, during 7° HDT, at 0 (supine rest) and in the final minute of each level of LBNP we will draw blood to determine $S_{[ALD]}$, $S_{[ACE]}$, $S_{[ANG]}$, $P_{[Renin]}$, PRA, $P_{[ANG\ II]}$, $P_{[NE]}$, $P_{(38)}$, electrolytes, Cr and Osm. Urine samples will be collected just prior and after baroreflex/RAS LBNP protocol for electrolytes.

Statistical analyses: We use ANOVA as described in Protocols 1. **Sample Size** is based on calculations in Aim 1, as the Aim 1 variables are the more stringent.

Expected results, interpretation of data, limitations and anticipated problems: Based on our hypothesis, **we expect** that women with AE-PCOS will have greater RAS hormonal responses to LBNP, reflecting greater RAS activation. **We expect** that testosterone suppression will reduce PRA, $S_{[ALD]}$, $S_{[ANG\ II]}$, PRA and $P_{[Renin]}$ response to LBNP, suggesting lower RAS activation in both Control and AE-PCOS. **We expect** that increasing $P_{[Tfree]}$ and FAI will increase RAS hormone response to LBNP, reflecting greater RAS activation responses to LBNP in AE-PCOS. Since the methods to be used are in place in our laboratory, we don't anticipate any problems in performing the studies in this Aim.

Expected results, interpretation of data, limitations and anticipated problems: **We expect** AE-PCOS women will have greater resting MSNA compared to Controls. **We anticipate** that slopes for MSNA-DBP will be greater in AE-PCOS, indicating increased sympathetic BRS compared to Control. **We expect** that testosterone suppression will decrease slopes for MSNA-DBP in AE-PCOS, and testosterone administration will increase slopes for MSNA-DBP in both Control and AE-PCOS. In contrast, **we expect** reduced slopes of PI-SBP with modified Oxford and paced breathing, indicating decreased sympathetic and cardiovagal BRS in AE-PCOS women; **we expect** a steeper PI-SBP slope with androgen suppression, and a steeper PI-SBP slope with modified Oxford, as well as paced breathing and Valsalva in both groups. Since all methods to be used are in place in our laboratory, we don't anticipate any problems in performing the studies in this Aim.

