Statistical analyses: We use ANOVA as described in Protocols 1 & 2 to test changes in blood pressure, FMD and baroceptor sensitivity. **Sample Size** is based on calculations in Aim 1, as the Aim 1 variables are the more stringent.

Aim 3: **We expect** AE-PCOS women will have greater resting blood pressure compared to Controls. **We expect** that women with AE-PCOS will have greater RAS hormonal responses to LBNP, reflecting greater RAS activation. **We expect** that testosterone suppression will reduce PRA, $S_{[ALD]}$, $S_{[ANG\ II]}$, PRA and $P_{[Renin]}$ response to LBNP, suggesting lower RAS activation in both Control and AE-PCOS. **We expect** that increasing $P_{[Tfree]}$ and FAI will increase RAS hormone response to LBNP, reflecting greater RAS activation responses to LBNP in AE-PCOS. **We expect** Flow Mediated Vasodilation to be lower in the women with AE-PCOS compared to control women, and we expect the suppression of testosterone to eliminate this difference. **We expect** that increasing $P_{[Tfree]}$ and FAI will increase FMD in women with AE-PCOS, with little impact on Controls. **We anticipate** that women with AE-PCOS will have lower baroreceptor sensitivity, compared to Controls, and that this will be improved with testosterone suppression. Finally, we expect increasing $P_{[Tfree]}$ and FAI will increase baroreflex sensitivity in women with AE-PCOS, with little impact on Controls. Since the methods to be used are in place in our laboratory, we don't anticipate any problems in performing the studies in this Aim.

Aim 4. We expect that testosterone will be suppressed similarly during elagolix and ganirelix treatments. We will use Cronbach's alpha as a measure of internal consistency or reliability (95).

Aim 5. We expect black women with AE-PCOS will have greater resting blood pressure compared to white women with AE-PCOS. We anticipate that slopes for MSNA-DBP will be greater in black women with AE-PCOS, indicating increased sympathetic BRS compared to white women with PCOS.

PROCEDURES

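### The two-factor ANOVA does not match the diagnosis by Protocol by Day design, and names neither the suppression contrast nor the arm and day that serve as testosterone comparator

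*Combined protocol and SAP*

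**What the plan says.** The statistical analysis paragraph for Aim 1 in Section V.3 (Research Plan), repeated in Section V.12 (Statistical Considerations), says the regression slopes and resting MSNA "will be compared between treatment conditions (GnRH antagonist vs. GnRH antagonist+T and between groups (Control vs AE-PCOS) using a 2-way repeated measures ANOVA", followed by Tukey tests. Aim 2 reuses this: "We use ANOVA as described in Protocols 1". For Aim 3, Section V.3 says "We use ANOVA as described in Protocols 1 & 2 to test changes in blood pressure, FMD and baroceptor sensitivity", while Section V.12 uses the shorter Aim 2 sentence.

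The design is set out under Participants and Experimental Protocols in Section V.3. At consent, "subjects will be randomly assigned to take a GnRH antagonist with or without methyl testosterone". Women with and without AE-PCOS are split into two Protocols ("4 groups total, n=18 each) to be tested 3 times each"; 8 each in Aim 3). Day 1 precedes the antagonist in both Protocols. Protocol 1 continues on antagonist alone at Days 3 and 10. Protocol 2 has "GnRH antagonist alone (Day 3), GnRH antagonist + methyltestosterone (Day 10").

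Section V.1 (Statement of Purpose) puts androgen suppression at the centre of hypotheses 1A, 2A and Aim 3, and androgen administration at the centre of 1B and 2B.

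**The concern.** The analysis sentence is the only inferential model described for these outcomes. It names neither the three test days nor the randomised Protocol as such, and no contrast is tied to a day.

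Two things are at stake. First, the suppression hypotheses need an untreated state compared with a suppressed one, and no such test is written down. Second, the testosterone comparison can be made in two ways that estimate different things. Protocol 2 women at Day 10 can be compared with themselves at Day 3. That comparison mixes testosterone with about a week's more antagonist, and sometimes longer ("Subjects may be kept on Antagon for as long as 18 days if there is a challenge with experiment scheduling"), and with repeat testing. Or they can be compared with the women randomised to antagonist alone, who share the schedule. Only the second uses the randomisation. Leaving the choice open until the data are seen weakens whichever answer is reported.

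**Working it through.** **1. Design and analysis side by side.**

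| | Factors | Levels |
|---|---|---|
| Design | diagnosis; randomised Protocol; Day | 2 x 2 x 3 = 12 cells |
| Analysis text | condition; diagnosis | antagonist, antagonist+T; Control, AE-PCOS |

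**2. Two readings of the condition labels.**

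- *Hormonal states.* Both levels are suppressed. Day 1 is a scheduled baseline visit (Visit 4 in Research Design) but is not a named level, so the stated comparison contains no suppression contrast.
- *Randomised arms.* The labels also fit the two Protocols. Repeated measures then implies Day, and Day 1 is in the model. No contrast is named, so neither Day 3 minus Day 1 nor Day 10 between arms is identified as the test.

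The testosterone comparator's arm and day are unstated on both readings.

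**3. The plan's own power figure.** It gives 15 per group, two-sided alpha 0.01 and an effect (SD) of 0.39 (0.16), with power above 0.9 within groups and 0.80 between. Read as d = 0.39/0.16 = 2.44, power is about 1.00 for both. Read as d = 0.39, it is 0.11 paired and 0.06 two-sample. Neither reading reproduces the stated pair, so the figure does not reveal which contrast was powered. The present point does not rest on it.

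**4. Precision of the candidate contrasts.** Units are the between-woman SD at one visit; two-sided alpha is 0.01. The documents give no between-visit correlation, so r = 0.6 is assumed.

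- *Testosterone, within-woman (Day 10 minus Day 3).* SE = sqrt(2(1-r)/n). At n=18: sqrt(0.8/18) = 0.211, df 17. Detectable with 80% power: 0.80 SD at n=18, 0.90 at n=15, 1.43 at n=8.
- *Testosterone, randomised, within a diagnosis, Day 10 adjusted for Days 3 and 1.* Residual variance = 1 - 2r²/(1+r) = 1 - 0.72/1.6 = 0.55. SE = sqrt(2 x 0.55/n), which is 0.247 at n=18, df 2n-4. The noncentral t gives 0.89, 0.99 and 1.48 SD, but simulated power at those effects is only about 0.72 to 0.78, because the formula ignores chance imbalance in the covariates. Simulation puts 80% power at about 0.92 (n=18), 1.03 (n=15) and 1.6 SD (n=8).
- *Testosterone, randomised, AE-PCOS versus Control.* SE = sqrt(4 x 0.55/n). At 15 per cell: 0.383, df 54. Power for a 1.0 SD difference is at most about 0.48.
- *Suppression (Day 3 minus Day 1), Protocols pooled.* Within a diagnosis, SE = sqrt(0.8/N); versus Control, sqrt(1.6/N). At N=36 per diagnosis: 0.149 and 0.211, detectable 0.54 and 0.74 SD. At N=30: 0.163 and 0.231, detectable 0.59 and 0.81 SD.

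**5. Illustration of the confounding.** Suppose testosterone has no effect but the outcome drifts between Days 3 and 10. At n=18 and r = 0.6 (SE 0.211), the within-woman test rejects in the direction of the drift 1.6% of the time at 0.1 SD drift, 6.7% at 0.25 SD and 33% at 0.5 SD. For r from 0.4 to 0.8 the last two become 4.5% to 14.5% and 21% to 67%. The randomised Day 10 contrast stays at about 1%. The documents give neither drift nor correlation, so these rates show direction only.

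**The case against.** The strongest defence is that the sentence is shorthand for a fuller model. The condition labels match the randomised arms, so 2-way may count the two between-woman factors and repeated measures the three visits. The sample-size text powers within-group comparisons separately from between-group ones. The Aim 4 paragraph refers to ganirelix-induced changes found in Aims 1 to 3. The Aim 3 sentence in Section V.3 speaks of changes and cites both Protocols. Within-woman comparisons are plainly intended.

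Much of this stands, and it rules out stronger readings. A reader might infer that the plan cannot answer the suppression hypotheses, that Day 1 data would go unanalysed, or that the confounded testosterone comparison has been chosen. The documents support none of these; they leave the matter open. What the defence does not supply is a stated test: the Aim 4 remark concerns hormone levels, and none of these passages specifies a contrast for the BP, MSNA or baroreflex outcomes.

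A reader might also infer real doubt about who receives testosterone. One sentence covering Aims 1 to 3 says "Subjects will also ingest a testosterone pill for seven days" without excepting the antagonist-only arm, and testosterone is Protocol 2 under Experimental Protocols but Group 1 under Research Design. Since the randomisation text, both study-design paragraphs and the alternative visit list all describe an antagonist-only arm, these are editorial conflicts.

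**Conclusion.** The concern holds as an ambiguous specification that should be fixed before the outcomes are analysed. The two-factor description does not carry the three-factor design, no untreated-versus-suppressed test is stated for 1A, 2A or Aim 3, and the arm and day of the testosterone comparator for 1B and 2B are not given. This follows from the text alone.

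The numerical consequences depend on the assumed correlation of 0.6. The false-positive rates also depend on an assumed drift and should carry no weight as estimates. They show only that the two permitted testosterone comparisons can lead to different conclusions from the same data, and that the randomised one is protected against shared time effects.

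**What to change.** In Sections V.3 and V.12, and by reference for Aims 2 and 3, replace the 2-way ANOVA with a mixed model or mixed ANOVA containing diagnosis, Protocol and Day, and name two contrasts:

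- **Suppression:** Day 3 minus Day 1, pooled over Protocols, within AE-PCOS and versus Control, labelled as an uncontrolled before-after contrast.
- **Testosterone:** antagonist+T versus antagonist alone at Day 10, between randomised Protocols, adjusted for earlier visits (for example Day 3), within AE-PCOS and versus Control.

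As editorial points, reconcile the Protocol and Group labels, and reconcile the testosterone-pill sentence with the antagonist-only arm.

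No new visits or women are needed. The cost is precision for testosterone. Relative to the within-woman test, the detectable effect within a diagnosis rises by about 0.12 SD at n=18 (0.92 - 0.80), 0.13 at n=15 (1.03 - 0.90) and 0.17 at n=8 (1.6 - 1.43). These figures adjust for both earlier visits; adjusting for Day 3 alone would be somewhat less precise. The plan should say openly that the versus-Control testosterone contrast is weak.
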